4.4.6. Visit 5: Day -7 – Phone visit

Visiting window: +/- 3 days.

Visit will be performed as a remote telephone visit by an investigator or a study nurse. Any problems with compliance or other questions regarding the protocol will be discussed.

At this telephone visit the subject will be reminded to detach the accelerometer for measurement of physical activity after a total of one-week registration. Subjects will be reminded to return the accelerometer and ECG using the two pre-paid envelopes previously obtained. Follow up regarding process and collections of urine samples for DLW measurements will be done.

Any changes to or new adverse advents will be documented. Subject will be reminded of the following study visit.

Study code: ATLAS

Version No: 14.9

Date: 2021-02-01

The day before visit 6 subjects will receive a text message to their mobile phone with a reminder regarding fasting blood samples and DLW measurements on visit 6.

4.4.7. Visit 6: Day 0 – Randomization and start of intervention

Visiting window: +/- 3 hours compared to study visit on day -13. CT- and DXA-scans to be performed +/- 3 days from visit 6 on day 0.

Study center visit where subjects will meet with an investigator and a study nurse. At this visit randomization will take place and intervention will start.

The last urine sample (sample 7) will be collected at the study center in the morning. The subject will return the 4 urinary samples collected from the doubly labeled water measurements at home. The accelerometer used for the basal measurement of physical activity and the ECG equipment is also to be returned if not already sent via prepaid envelope. The subject is required to have had an overnight fast before this visit, this due to the blood sampling. Subjects are to answer the first Dietary Short Questionnaire (SDQ) digitally either using their own mobile phone or a specified computer at the study center.

Any changes to or new adverse advents will be documented.

During the visit the following examinations will be performed:

- Physical examination
- Blood pressure
- Body weight
- Fat mass, water mass and fat free mass will be measured using BIA
- Waist circumference
- Fasting venous blood sampling according to section 7.1.2.6. Blood sampling
- Fasting capillary blood sample for measurement of glucose level according to section 7.1.2.6. Blood sampling

Subjects are included as they are found to be eligible for inclusion in the study. After the baseline period at day 0 subjects will be randomized in a 1:1 ratio into either the intervention group (heavy weight vest) or the control group (light weight vest). Randomization will be through permuted blocks, stratified by age 18-50 years, age 51-65 years and gender performed in the electronic Case Report Form (eCRF) using a built-in function for the purpose. If a subject discontinues their study participation, their randomization code will not be reused, and the subject will not be allowed to reenter the study again.

Study intervention will start directly after blood sampling and randomization. Subjects will get a randomized three-character code as a randomization number to be used throughout the study. The randomization number will be linked to the subject's enrolment number received at screening. Study subjects will be randomized either to the control or intervention group. The intervention group will obtain a weight vest with 11 % of the subject's body weight (heavy weight vest) and the control group will obtain a weight vest with 1 % of the subject's body weight (light weight vest). The vest is to be worn 8 hours each day for the following 5 weeks. The vest is only to be worn during waking hours. Subjects are also required to be in a standing position for at least 2 hours per day while wearing the vest for the following 5 weeks. Subjects are to be instructed not to wear the vest during upcoming study visits.

Study code: ATLAS
Version No: 14.9

Date: 2021-02-01

Each subject will be informed about the protocol for the second measurement of doubly labeled water (DLW). For the second DLW measurement subjects will then receive one container for collection of the first urine sample at home and a bottle containing a calculated dose of doubly labeled water. Further detailed written instructions on how to consume the prearranged dose of DLW and how to collect and store the urine sample will also be given.

Close to this visit (+/- 3 days) participants will go through a CT- and DXA-scan. This to get baseline values of fat depots, liver fat and body composition. Procedures will be performed by experienced personnel operating the CT- and DXA-scan. Subject will be reminded of the following study visit.

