^{*} Telephone visit for participants. This to prevent mistakes, to document adverse advents and to minimize the loss to follow-up. Visits also to be performed in the evenings on the starting day of the doubly labeled water measurements to ensure compliance to protocol.

^{**} Physical visit for participants at study center.

Study code: ATLAS
Version No: 14.9

Date: 2021-02-01

Week -2 – Day -13 (Visit 4): Study center visit. Enrolled participants will receive equipment and information needed for first measurements with ECG and accelerometers. Collection of the second urine sample for the first DLW measurement. Obtainment of equipment and information needed for the first measurements with DLW. Measurements of body weight and body composition.

Week -1 - Day -7 (Visit 5): Telephone visit.

Week 0 – Day 0 (Visit 6): Study center visit. Fasting blood sampling, CT abdomen, DXA. Measurement of body weight, blood pressure, body composition. Collection of the last urine sample for the first DLW measurement. SDQ registration. Randomization and adding of weight vest. Obtainment of material and information for the first day of the second DLW measurement.

Week 1 - Day 7 (Visit 7): Telephone visit.

Week 2 – Day 14 (Visit 8): Telephone visit. Participants will collect the first urine sample for the second DLW measurement at home and thereafter drink the second dose of DLW. This after an evening telephone visit from study personnel repeating the procedure protocol and explaining any uncertainties.

Week 3 – Day 15 (Visit 9): Study center visit. Fasting blood sampling. Participants will receive equipment and information needed for second measurements with ECG and accelerometers. Collection of the second urine sample for the second DLW measurement. Obtainment of equipment and information needed for the second measurements with DLW. Measurements of body weight, body composition and waist circumference.

Week 3 - Day 21 (Visit 10): Telephone visit.

Week 4 – Day 28 (Visit 11): Study center visit. Collection of the last urine sample for the second DLW measurement. Measurements of body weight, waist circumference and body composition. SDQ registration.

Week 5 – Day 35 (Visit 12): Study center visit. Fasting blood sampling, CT abdomen, DXA. Measurements of body weight, waist circumference, blood pressure and body composition. Removal of weight west.

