4.4.13. Visit 12: Day 35 – End of intervention

Visiting window: +/- 2 days compared to day 0. CT- and DXA-scans to be performed +/- 3 days from visit 12 on day 35.

Subjects will be entitled to another visit with an investigator and a study nurse 5 weeks after the start of intervention. The subject is required to have had an overnight fast before this visit and not have eaten anything before the study visit, this due to the blood sampling. Study subjects will have worn the vests for 8 hours the day before, but they will not wear it during the visit the morning of day 35.

The research subject will be questioned regarding possible adverse events.

The following examinations will be performed:

- Physical examination
- Blood pressure
- Body weight
- Fat mass, water mass and fat free mass will be measured using BIA
- Waist circumference
- Fasting venous blood sampling
- Fasting capillary blood sample for measurement of glucose level

Close to this visit (+/- 3 days) participants will go through a CT- and DXA-scan. Procedures will be performed by experienced personnel operating the CT- and DXA-scan.

The day before visit 13 subjects will receive a text message to their mobile phone with a reminder regarding the fasting blood samples on visit 13.

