7.1.2.2. Dual-energy X-ray absorptiometry (DXA)

Dual-energy X-ray absorptiometry (DXA) scans are to be performed at study day 0 (+/- 3 days) and day 35 (+/- 2 days). A DXA-scan of the model Lunar iDXA, encore version 16, SP 1, will be used and the procedure shall be carried out according to local routines to obtain a body composition representation which can differentiate between body fat and fat free mass. Measurements will provide absolute levels of in fat mass (g) and fat free mass (g). The total time for one scan is expected to take 15 minutes. Images will be stored locally on a computer connected to the DXA-scan and will not be accessible to unauthorized personnel. Images and data will be exported for further data analysis. DXA-scan will be executed at Center for Health and Performance at University of Gothenburg. [name], Center for Health and Performance, University of Gothenburg, is responsible for the execution and interpretation of these measurements.

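### The CT and DXA windows allow a baseline scan up to 3 days after the vest is put on and a final scan after it comes off, which dilutes the scan-based exploratory endpoints

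*Protocol*

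**What the plan says.** **Start of the intervention.** Protocol section 4.4.7 says of visit 6 (day 0): "At this visit randomization will take place and intervention will start". It adds: "Study intervention will start directly after blood sampling and randomization". Blood sampling and randomisation must come first; the scans are not named as a condition.

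**Baseline scans.** The same section gives the window as "CT- and DXA-scans to be performed +/- 3 days from visit 6 on day 0" and later repeats it: "Close to this visit (+/- 3 days) participants will go through a CT- and DXA-scan". Their purpose is explicit: "This to get baseline values of fat depots, liver fat and body composition". The flow chart in section 4.2 and the methods in sections 7.1.2.2 (DXA) and 7.1.2.3 (CT) give the same 3 days either side of day 0.

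**Final scans.** Section 4.1 lists, for the day 35 visit, "Removal of weight west". Section 4.4.13 has "CT- and DXA-scans to be performed +/- 3 days from visit 12 on day 35", and visit 12 itself may move by 2 days. The flow chart also gives 3 days, and section 7.1.2.3 gives 3 days around day 35 for CT. For DXA, section 7.1.2.2 differs: "scans are to be performed at study day 0 (+/- 3 days) and day 35 (+/- 2 days".

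**Baseline in general.** Sections 4.4.7 and 6.1 both place randomisation after the baseline period.

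**The concern.** A baseline should be untouched by the treatment. Here a participant may be randomised, wear the assigned vest for up to three days and only then have the scan from which change is calculated. Whatever the vest has already done is then subtracted from its own effect. A final scan after removal may miss part of the effect if it recedes, and one taken early misses days of loading. Because the windows extend in both directions, the exposure between the two scans also varies from person to person.

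This affects total, subcutaneous and visceral fat, the subcutaneous-to-visceral ratio, liver fat and the topographic CT analysis (objectives 5 to 10), and DXA fat and fat-free mass (part of objective 11). Section 2.2 names a decrease in visceral fat as something the trial specifically wants to examine. Later analysis cannot supply a pre-vest scan that was never taken.

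**Working it through.** **Inputs.** Vest start: day 0 (4.4.7). Baseline scan: day -3 to day +3 (4.2, 4.4.7, 7.1.2.2, 7.1.2.3). Planned end: day 35. Visit 12: day 33 to 37 (4.4.13). Final scan: 3 days either side of visit 12 (4.2, 4.4.13); day 32 to 38 for CT (7.1.2.3); day 33 to 37 for DXA (7.1.2.2). The protocol states no effect size, standard deviation or power for any scan endpoint, so there is no figure of its own to reproduce for them.

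**Dilution from a late baseline.** Assume the between-arm difference grows linearly over 35 days. A baseline on day *b* > 0 leaves (35 - *b*)/35 of it measurable.
- Day +1: 34/35 = 97.1%
- Day +2: 33/35 = 94.3%
- Day +3: 32/35 = 91.4%, a loss of 3/35 = 8.6%

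The protocol does not say how scans will be distributed. If they are spread evenly over the seven days, four days (-3 to 0) hide nothing and three hide 1, 2 and 3 days. The mean is (1 + 2 + 3)/7 = 0.86 day, and 0.86/35 = 2.4%.

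**Exposure between scans.**
- Visit 12 on day 35, final scan within 3 days of it: the scans are 32 - 3 = 29 to 38 + 3 = 41 days apart. The shortest case contains 29/35 = 83% of the planned loading.
- DXA under 7.1.2.2: 33 - 3 = 30 to 37 + 3 = 40 days apart.
- If the final window follows the actual date of visit 12: final scans fall on day 33 - 3 = 30 to 37 + 3 = 40, the scans are 27 to 43 days apart, and 27 to 37 vest days lie between them.

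The loss from a scan after vest removal cannot be sized, because the protocol gives no rate at which an effect would recede.

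**Power, as illustration only.** Borrow the body-weight assumptions of section 9.3: difference 1.6, SD 2, 25 per group, alpha 0.05 (two-sided assumed). Normal approximation: *n* = 2 × (1.96 + 0.842)² × 2²/1.6² = 24.5, so 25 per group, which reproduces the stated number. Power at 25 is Φ(1.6/(2 × √(2/25)) - 1.96) = 80.7%. Multiplying the difference by the fractions above gives 78.5% if every baseline scan were one day late, 76.0% if two and 73.4% if three. An even spread averages less than one day, so the loss would be about two points or less.

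**The case against.** The best defence is that the window is a booking tolerance, not a planned post-vest baseline. The figure 3 legend in section 4.1 puts the scans on days 0 and 35, and the day 0 entry there lists CT and DXA ahead of randomisation and vest fitting. DXA is done at a separate university centre (7.1.2.2), so same-day scanning may be hard to arrange. This shows intent, but a list order and a nominal day do not bind a site that has an explicit window running to day +3.

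The second defence is that the consequence is limited. Section 9.2.1 declares all secondary endpoints exploratory, and dilution does not by itself create false positives. Both points stand and keep the matter in proportion.

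Some stronger readings are tempting but unsupported.
- A reader might take 8.6% or 83% as the expected loss. Both are extremes for one participant, and the second needs the latest baseline and an early final scan in the same person.
- A reader might state that final scans run from day 30 to day 40. That holds only if the window follows the actual visit 12 date; sections 7.1.2.2 and 7.1.2.3 count from day 35.
- A reader might infer biased reading because the arm is already known. The participant knows, but no route to a biased value is shown. CT images are pseudonymised and sent to another university for automated analysis (7.1.2.3), and no section says that DXA readers know the arm.
- A reader might expect rapid early shifts in water or glycogen to enlarge the loss. The protocol gives no such time course.

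**Conclusion.** The protocol permits baseline CT and DXA up to 3 days after randomisation and vest start, contrary to its own statement that randomisation follows the baseline period. It also permits final scans after vest removal: up to 3 days for CT, and 2 or 3 days for DXA depending on the section. The final DXA window is a plain contradiction between section 7.1.2.2 on one side and section 4.4.13 and the flow chart on the other.

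The result is dilution and uneven exposure in the scan-based exploratory endpoints. Under a linear effect, the late baseline costs at most 8.6% for one participant, and about 2.4% on average if scans are evenly spread; both the linearity and the spread are assumptions.

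A reader might conclude that the main result is at risk. It is not: body weight, impedance and waist are measured at the day 0 and day 35 visits and do not use the scans. The point is worth correcting because the correction is cheap, not because the loss is large.

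**What to change.** 1. Require baseline CT and DXA on day -3 to day 0, completed before randomisation and vest fitting.
2. Require final CT and DXA no later than visit 12, before vest removal and as close to that visit as booking allows. An early final scan still loses some loading (three days early: 32/35 = 91.4%), so closeness matters.
3. Reconcile the final DXA window across sections 4.2, 4.4.13 and 7.1.2.2, and state for both modalities whether it is counted from day 35 or from the actual date of visit 12.

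The wording changes fall in the section 4.2 flow chart and in sections 4.4.7 (two places), 4.4.13 (two places), 7.1.2.2 and 7.1.2.3.

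**Cost.** Scanner booking becomes tighter. In addition, exclusion criterion 7 in section 5.2 rejects a weight change above 3 kg between day -21 and day 0, which is settled only at the day 0 weighing, so a few people may be scanned, with the small radiation dose noted in section 2.3, and then excluded. Scanning on day 0 after that check and before randomisation avoids this where it can be arranged. Sample size and the primary analysis do not change.

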4.4.8. Visit 7: Day 7 – Phone visit

Visiting window: +/- 3 days.

Telephone visit by an investigator or a study nurse. Any problems with compliance will be discussed. At this meeting the subject will also be questioned regarding possible adverse events.

The day before visit 8 subjects will receive a text message to their mobile phone with a reminder regarding visit 8 and the DLW measurements.

Study subjects will continue to wear the vests for 8 hours a day. Subject will be reminded of the following study visit.

4.4.9. Visit 8: Day 14 – Second DLW measurements

Visiting window: Telephone call between 17:00 - 22:00 hours. Must be executed exactly on Day 14 compared to Day 0.

Telephone visit that shall be performed in the afternoon or evening. Study personnel will call subjects and repeat the DLW procedure to be performed by the subjects later the same evening. It is crucial that subjects follow the protocol and they shall first be informed on how to collect the first urine sample (sample 8). Secondly, they shall be informed on how to consume the calculated dose of doubly labeled water for the second DLW measurement. The doubly labeled water should be consumed by the subject as the last consumption of the day. The subject will be reminded of visit 9 at the study center in the morning the following day.

Any changes to or new adverse advents will be documented. Study subjects will continue to wear the vests for 8 hours a day. Subject will be reminded of the following study visit.

The day before visit 9 subjects will receive a text message to their mobile phone with a reminder regarding the DLW measurements and fasting blood samples on visit 9.

4.4.10. Visit 9: Day 15 – Second DLW measurements continued

Visiting window: Morning visit the day after visit 8.

Study center visit planned in the morning the day after visit 8. The second voiding of the day should be collected at the study center (sample 9) the morning after drinking the doubly labeled water dose. It is important that the first voiding of the day is not collected as sample 9. However, it is not as important if it is the second or third voiding of the day that is collected as sample 9. Subjects will receive material for collection of urine sample 10-13 at home. Each subject will

Study code: ATLAS
Version No: 14.9

Date: 2021-02-01

receive four containers for collection of urine samples and detailed oral and written instructions on how to collect and store the urine samples.

Subjects will receive an accelerometer for the second measurement of physical activity that will be worn on day 15 to 21. The accelerometer will be attached by study personnel and the subject will be instructed how to reattach the device if so to be needed. The research subject will be instructed to wear the accelerometer 24 hours per day for seven days. During the visit a study nurse will attach a portable ECG monitor for a second 24-hour ECG recording. After attachment of the ECG the subject is required to lay down for 1 hour to get a standardized registration, this shall be done at the study center. The subject will receive two pre-paid envelopes in which the ECG monitor and the accelerometer are to be returned after each registration is completed. The subject is required to have had an overnight fast before this visit, this due to the blood sampling. Any changes to or new adverse advents will be documented.

The following examinations will be performed:

- Physical examination
- Blood pressure
- Body weight
- Fat mass, water mass and fat free mass will be measured using BIA
- Waist circumference
- Fasting venous blood sampling
- Fasting capillary blood sample for measurement of glucose level

Study subjects will continue to wear the vests for 8 hours each day. Subject will be reminded of the following study visit.

Study code: ATLAS
Version No: 14.9

Date: 2021-02-01

Second measurement with DLW and second ECG registration

Urinary samples will be stored by subject in a home freezer after collection. The containers for collection of urine should be dry and have an airtight lock. They should not be rinsed with water before collection of urine since this can disturb the analysis.

Day 14

- On the evening of day 7, before going to bed (usually between 22:00 and 24:00) the subject collects a voiding as a background sample (sample 8) at home
- Afterwards the subject drinks the bottle with the calculated dose doubly labelled water
 as the last consumption of the day. The water is consumed straight from the bottle and
 afterward the bottle is filled with ~50 mL of tap water, closed with a screw cap and
 shaken, and subsequently the rinsing water is consumed as well.
- Procedures during this day are to be performed after a telephone visit from study personnel informing about the protocol

Day 15

- In the morning the second voiding of this day is collected (sample 9) and the body weight is thereafter measured. This step is to be performed at the study center.
- In the morning an ECG monitor will be attached and subjects are required to lay down to get a standardized registration. This shall be done at the study center.
- In the evening of this day another voiding is collected (sample 10) at home.

Day 22

- An early morning voiding is collected on day -6 (sample 11) at home.
- An evening voiding is collected on day -6 (sample 12) at home.

Day 27

- An evening voiding is collected on day -1 (sample 13) at home.

Day 28

- An early morning voiding is collected on day 0 (sample 14) at the study center.

4.4.11. Visit 10: Day 21 - Phone visit

Visiting window: +/- 3 days.

Visit will be performed as a remote telephone visit by an investigator or a study nurse. Any problems with compliance or other questions regarding the protocol will be discussed.

At this telephone visit the subject will be reminded to detach the accelerometer for measurement of physical activity after a total of one-week registration. Subjects will be reminded to return the accelerometer and ECG using the two pre-paid envelopes previously obtained. Follow up regarding process and collections of urine samples for DLW measurements will be done. Any changes to or new adverse advents will be documented.

Study subjects will continue to wear the vests for 8 hours each day. Subject will be reminded of the following study visit.

4.4.12. Visit 11: Day 28 – End of second DLW measurement

Visiting window: +/- 3 hours. Compared to visit 9 on day 15.

Study code: ATLAS Version No: 14.9

Date: 2021-02-01

Visit at the study center. The last urine sample (sample 14) will be collected at the study center in the morning. The subject will return the 4 urinary samples collected from the doubly labeled water measurements at home. The accelerometer used for the basal measurement of physical activity and ECG are also to be returned if not already sent via prepaid envelope. Any changes to or new adverse advents will be documented. Any problems with compliance will be discussed. Subjects are to answer the second Dietary Short Questionnaire (SDQ) digitally either using their own mobile phone or a specified computer at the study center.

During the visit the following examinations will be performed:

- Body weight
- Fat mass, water mass and fat free mass will be measured using BIA
- Waist circumference

Study subjects will continue to wear the vests for 8 hours each day. Subject will be reminded of the following study visit. The day before visit 12 subjects will receive a text message to their mobile phone with a reminder regarding the fasting blood samples on visit 12.

